missed data points, in part because the participation time is not appropriately weighted. For these reasons, time to ESRD provides a secondary outcome that obviates most of the problems inherent in a slope-based analysis. Time to ESRD or 50% decline in baseline GFR or 25 ml/min/1.73m² decline in baseline GFR is particularly attractive as a secondary outcome for the FSGS/MCD study because, in general, time to a specified event constitutes a clearer outcome than a slope. In addition, time to event analysis does not force a functional form (i.e. linear decline) on the process of progression. It is likely that the analytic problems associated with a particular measurement technique are minimized when comparing values for an individual over time. Censoring methods are readily applicable to participants who depart early. Lastly, time to ESRD (i.e. initiation of renal replacement therapy for usual clinical indications) is the most important clinical and economic consequence of FSGS/MCD and MN. This time can be ascertained for participants even after formal completion of the proposed study.

3.E.2. Secondary Outcome Variables

Composite of the following events will be considered as secondary outcomes of the NEPTUNE main cohort study. Additional CRFs or appropriate source documentation may be required for further clarification and/or event adjudication for the following ‘secondary outcomes of special interest’:

- (1) Quality of Life: Patient-reported outcome will be assessed using the Patient Reported Outcome Measurement Information System (PROMIS) from ages 8 and above and parent proxy PROMIS measures will be completed for ages 0-10. Overlap in ages 8 to 10 years allows the complete ascertainment of this assessment in children who may find self-reporting difficult due to delayed reading skills.
- (2) New Onset Diabetes: New-onset diabetes is a diagnosis of diabetes as indicated by one or more of the following that was not present at the time of NEPTUNE enrollment.
 - a) Documented diagnosis of diabetes in the medical record
 - b) Casual (non-fasting) blood glucose > 200 mg/dL
 - c) Fasting blood glucose > 126 mg/dL
 - d) 2 hour glucose > 200 after oral glucose tolerance test
 - e) chronic use (> 6 months) of hypoglycemic therapy outside of pregnancy
 - f) Hemoglobin A1C \geq 6.5% (94)
- (3) Malignancies: Any cancer diagnosis of the skin, hematopoietic system, or solid organ after enrollment in NEPTUNE

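### New-onset diabetes can be scored on one unconfirmed glucose value or a gestational diagnosis, because only one of its six alternative criteria requires persistence and excludes pregnancy

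*Protocol*

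**What the plan says.** New-onset diabetes is item (2) in the list of secondary outcomes in Protocol section 3.E.2. The criteria are joined as alternatives: "New-onset diabetes is a diagnosis of diabetes as indicated by one or more of the following that was not present at the time of NEPTUNE" (study entry). The ones that matter here are:

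- The chart route, item (a): "Documented diagnosis of diabetes in the medical record"
- The random-sample route, item (b): "Casual (non-fasting) blood glucose > 200 mg/dL"
- The fasting-sample route, item (c): "Fasting blood glucose > 126 mg/dL"
- The tolerance-test route, item (d): "2 hour glucose > 200 after oral glucose tolerance test"
- The treatment route, item (e): "chronic use (> 6 months) of hypoglycemic therapy outside of pregnancy"

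Item (f) is a hemoglobin A1C threshold of 6.5% or more. Items (b), (c) and (d) are bare thresholds with no repeat, duration or pregnancy condition. Item (a) does not restrict the type of diabetes. The lead-in to the whole list of secondary outcomes adds: "Additional CRFs or appropriate source documentation may be required for further clarification and/or event adjudication". No adjudication rule for diabetes follows.

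**The concern.** The criteria are alternatives, so the limits written into (e) bind only a participant whose sole evidence is drug therapy. Anyone who also has one glucose value above a cut is an event whatever (e) says.

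This matters in this population. Section 1.A describes prolonged high-dose steroids as a mainstay of treatment. Section 2.A.3 says children routinely receive 8 to 12 weeks of corticosteroids, which is well short of the 6 months in (e). Section 3.C.2 collects glucose from chart metabolic panels and updates pregnancy history at follow-up visits. Brief steroid-related rises and gestational values can therefore enter the data and qualify.

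The reported diabetes rate would then combine two different things, and it would depend partly on how often glucose is measured. Participants who are sampled more often have more chances to qualify, so a comparison of diabetes rates between groups could partly reflect sampling.

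**Working it through.** **1. The rule applied to records.** The rule is (a) or (b) or (c) or (d) or (e) or (f). The records below are hypothetical, and none meets any criterion at enrollment.

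| Record | Item (e) | Other item met | Scored |
|---|---|---|---|
| One casual glucose of 215 mg/dL early in steroid treatment, three weeks of insulin, normal afterwards | not met (under 6 months) | (b) | event |
| Gestational diabetes entered in the chart during follow-up | not met (pregnancy) | (a) | event |
| Pregnant participant with a 2-hour value of 205, if a tolerance test was done for clinical reasons | not met (pregnancy) | (d) | event |
| Fasting glucose 122 at entry and 128 later, true level unchanged | not met (no therapy) | (c) | event |

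The first two records carry the point. The third needs a tolerance test, which the protocol does not schedule. The fourth is ordinary noise around a cut-point, but a repeat requirement would reduce it.

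**2. How far draw count drives the rate.** The protocol gives no diabetes rate to reproduce and no glucose distribution, so this step is an illustration on assumptions.

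Inputs from the protocol:
- The fasting cut is 126 mg/dL.
- Section 3.E.5.n says glucose is measured annually, which gives three follow-up values (months 12, 24 and 36).
- Section 3.C.2 schedules fasting blood at each follow-up visit V2 to V8, which gives seven (months 4, 8, 12, 18, 24, 30 and 36). Its list of central assays at those visits does not name glucose, so seven is an upper case for scheduled fasting values.

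Assumptions not in the protocol:
- True fasting glucose is constant over time and normal across participants, truncated at 126, with mean/SD of 95/10, 100/12 or 105/14 mg/dL.
- Each reading equals the true value × (1 + error), where errors are independent with CV 5% or 8%.
- The baseline reading is at or below 126.

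The quantity simulated is the percentage of these stable participants with at least one follow-up reading above 126, and with at least two. The lower figure in each cell is for CV 5% and the higher for CV 8%. Simulation error is about 0.1 percentage point.

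| Mean/SD | 3 draws, any one | 3 draws, two or more | 7 draws, any one | 7 draws, two or more |
|---|---|---|---|---|
| 95/10 | 0.6–2.1% | 0.1–0.3% | 1.2–4.1% | 0.4–1.1% |
| 100/12 | 2.8–6.4% | 0.6–1.2% | 4.9–11.1% | 2.0–4.3% |
| 105/14 | 6.1–11.3% | 1.4–2.6% | 10.0–18.8% | 4.6–8.6% |

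Going from three draws to seven raises the single-value rate by a factor of about 1.6 to 2 (for example 10.0/6.1 = 1.6 and 1.2/0.6 = 2) with no change in anyone's true glucose. A two-value rule cuts the rate by between about half (18.8% to 8.6%) and five-sixths (0.6% to 0.1%).

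The simulation covers criterion (c) only. Steroid-related and gestational events under (a), (b) and (d) would add to it, by an amount the documents do not allow one to estimate.

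**The case against.** The strongest reply is that there is no contradiction. A list of alternative evidence routes may give each route its own qualifier. Drug use is indirect evidence of diabetes, so a stricter condition on (e) makes sense, and the protocol never says that condition was meant for the glucose items. That is correct. A reader might infer that 6-month persistence and the pregnancy exclusion are limits on the whole definition which the other items evade, but the text attaches them to (e) alone. What stands is that they exclude nobody who also meets another item, and the protocol does not say that this is intended.

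A second reply is that steroid hyperglycemia is a real treatment complication. Section 1.B names metabolic complications among the secondary outcomes, so counting it may be the aim. This is fair, and it is a reason to keep such events visible. It does not justify labeling them new-onset diabetes.

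Third, the heading speaks of a diagnosis, and the lead-in allows for adjudication. But the diagnosis is defined as whatever the list indicates, and adjudication is optional with no diabetes rule. Confirmation detail may sit in the case report forms or Manual of Procedures. Even so, the definition applied as written gives the wrong classification, which goes beyond missing detail.

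A reader might also infer that the treatment comparisons under Hypothesis 7 are distorted. They are not: section 1.C.3 lists that composite as vascular thrombosis, biopsy complications, infection and death, without diabetes. Finally, taking seven fasting glucose values as the base case would overstate the size, given the annual schedule in section 3.E.5.n.

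**Conclusion.** The point holds in limited form. As written, section 3.E.2(2) scores new-onset diabetes on one unconfirmed value under (b) to (d), or on a gestational diagnosis under (a), for participants who fail the only criterion that requires persistence and excludes pregnancy. The logical part follows from the text alone. The size does not: the ranges of about 0.6 to 11% (three draws) and 1 to 19% (seven draws) rest entirely on the assumed glucose means, SDs and within-person variation, and they describe the fasting criterion only. The effect is confined to one secondary outcome. No primary outcome, sample size or power statement depends on it, so this is a minor but worthwhile correction.

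**What to change.** 1. Move the pregnancy exclusion from (e) into the heading sentence of item (2), so that it covers all six criteria, including a gestational diagnosis under (a).
2. Count (b), (c) or (d) as new-onset diabetes only when a second qualifying glucose value is recorded on a different day, or when the participant also meets (a), (e) or (f). Those three continue to qualify on their own. Leave (f) unchanged, since nothing here shows it to be defective.
3. Report unconfirmed single-value hyperglycemia as a separate category, so that any steroid-toxicity signal is kept.

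If the sponsor does want every hyperglycemic value counted, the alternative is to say so and rename the outcome.

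The cost is wording in the protocol, case report form and analysis plan, using glucose and pregnancy data already collected. The downside is fewer diabetes events, with some true cases dated later because they wait for a second value.

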- (4) Infections, Serious and Systemic: Infections including one of the following:
 - a) Documented diagnosis of infection of the skin or subcutaneous tissue (e.g. cellulitis), vascular system, peritoneum, or any vital organ requiring the use of parenteral antibiotics and/or oral antibiotics alone or in combination for a treatment interval of \geq 72 hours.
 - b) Hospitalization for treatment of infection
- (5) Thromboembolic Events: Documented diagnosis of one of the following:
 - a) Embolic cerebrovascular accident
 - b) Deep venous thrombosis
 - c) Renal vein thrombosis or
 - d) Pulmonary embolus
- (6) Hospitalization: Documented hospital admission, including observation for \geq 24 hours.

- (7) Emergency Department/ Observation Unit Visit: Documented visit to an emergency department or observation unit that does not lead to hospitalization and is less than 24 hours.
- (8) Acute Kidney Injury: Documented diagnosis of acute kidney injury as defined by the KDIGO criteria (Kidney Disease: Improving Global Outcomes (KDIGO) Acute Kidney Injury Work Group. KDIGO Clinical Practice Guideline for Acute Kidney Injury. *Kidney inter., Suppl.* 2012; 2: 1–138) and/or renal failure requiring renal replacement therapy <3 months.
- (9) End-Stage Renal Disease (ESRD): Documented chronic dialysis or transplant shall be considered ESRD for the purposes of the NEPTUNE study, a final renal outcome.
- (10) Death:
 - a) Infection-related Death. Documentation of death that is secondary to infection or sepsis.
 - b) Cardiovascular/Cerebrovascular-related Death: Documentation of death from at least one of the following:
 - i) Sudden death
 - ii) Myocardial infarction
 - iii) Congestive heart failure
 - iv) Primary intractable serious arrhythmia
 - v) Peripheral vascular disease
 - vi) Ischemic cerebrovascular accident
 - vii) Hemorrhagic cerebrovascular accident
 - viii) Thromboembolic event (e.g. pulmonary embolus, embolic cerebrovascular accident)
 - c) Malignancy-associated Death: Documentation of death secondary to cancer
 - d) Other Death: Documentation of death that does not fall into the above categories (e.g. primary respiratory failure).

3.E.2.a. Potential Data Sources and Ascertainment Strategy

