Data Sources: The NEPTUNE study participant contact pattern includes study visits and interim phone calls on an as-needed basis. For selected sites that have access to electronic administrative or billing records, regular searches of those data sources will be performed (e.g., quarterly) for their center's study participants. We will also explore the feasibility of using additional databases (National Death Index, USRDS and SRTR) to identify outcomes, although it is clearly recognized that there is often a long delay (e.g., 12-18 months or longer) in getting access to these files, which are updated annually and require additional governmental approval. In preparation for use of national data sources, the patients will be consented for the collection of the social security number for use in assessing vital status, ESRD status and transplant status using these national data sources.

Outcome Search Strategy: For potential clinical events that lead to hospitalization, we will acquire information from the study participant or their self-assigned proxy regarding the dates (admission and discharge) and hospital (name, address, phone number) where the patient was hospitalized. The scope of medical record acquisition is limited to the following events: hospitalizations, infectious episode requiring parenteral antibiotic therapy, outpatient cardiac catheterization, outpatient ECHO (MUGA or nuclear perfusion imaging), new onset heart failure, extended (>24 hour) ER or observation unit stay.

For potential clinical events that do not lead to hospitalization, we will acquire information from the study participant or their self-assigned proxy regarding the date of the potential event

and the location where the patient received treatment (e.g., outpatient clinic/surgicenter, address, phone number, and treating physician).

Patient Reported Information using SMS (text messaging): Participants in the cNEPTUNE cohort will report results of home urine protein testing, edema status, medication adherence, presence of infections, stressors, or allergies, and work and school absences. Tailored text messages will be sent to the designated parent/patient throughout the initial year of study participation.

3.E.3. Intra-renal Gene Expression Exposure Variables

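### The closed list of events for which medical records are obtained (Protocol 3.E.2.a) does not match the secondary outcomes defined in 3.E.2

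*Protocol*

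**What the plan says.** Protocol 3.E.2.a, under the outcome search strategy, states: "The scope of medical record acquisition is limited to the following events: hospitalizations, infectious episode requiring parenteral antibiotic therapy, outpatient cardiac catheterization". The list ends with "outpatient ECHO (MUGA or nuclear perfusion imaging), new onset heart failure, extended (>24 hour) ER or observation unit stay". For events without admission the same section says: "For potential clinical events that do not lead to hospitalization, we will acquire information from the study participant or their self-assigned proxy regarding" the date and the place of treatment, including address, phone number and treating physician.

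Protocol 3.E.2 defines the outcomes that this search is meant to find:

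- Infection, item (4)(a), is a documented diagnosis "requiring the use of parenteral antibiotics and/or oral antibiotics alone or in combination for a treatment interval of" at least 72 hours. Item (4)(b) adds admission for infection.
- Thromboembolism, item (5): "Thromboembolic Events: Documented diagnosis of one of the following", namely embolic stroke, deep venous thrombosis, renal vein thrombosis or pulmonary embolus. No admission is required.
- Emergency or observation care, item (7): "Documented visit to an emergency department or observation unit that does not lead to hospitalization and is less than 24 hours".
- Malignancy, item (3): "Any cancer diagnosis of the skin, hematopoietic system, or solid organ after enrollment in NEPTUNE".
- Cardiac disease appears only in item (10): "Cardiovascular/Cerebrovascular-related Death: Documentation of death from at least one of the following", with infarction, heart failure and arrhythmia among the causes.

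Two other places bear on access. The opening of 3.E.2 says that extra case report forms or source documents may be required for these outcomes. Section 4.J has participants sign an authorization that lets investigators see the records behind reported clinical events.

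**The concern.** The outcome definitions and the search strategy appear to have been written for different purposes. The list would suit a study with non-fatal cardiac outcomes. 3.E.2 has none, and it counts several complications that can be managed entirely as outpatient care.

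The affected outcomes serve Specific Aim 7. Hypothesis 7 asks whether a composite of thrombosis, biopsy complications, infection and death varies by baseline characteristics and treatment. If the chance that a thrombosis or infection is documented depends on where the participant was treated, the rates are exposed and so are the comparisons. The protocol expects such differences in setting: 4.B anticipates many participants referred from long distances, and 3.B.8 accepts that attributes such as race cannot be similarly distributed across sites.

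**Working it through.** The protocol gives no figure to reproduce. The check sets each outcome in 3.E.2 against the list in 3.E.2.a.

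| 3.E.2 outcome | Word "documented" used in a form that applies? | On the 3.E.2.a list? |
|---|---|---|
| Infection, parenteral antibiotics or admission | Yes for (4)(a) | Yes |
| Infection, oral antibiotics only, at least 72 hours, no admission | Yes | No |
| Thromboembolic event, admitted | Yes | Yes, as a hospitalization |
| Thromboembolic event, outpatient | Yes | No |
| Emergency or observation visit under 24 hours | Yes | No; only stays over 24 hours |
| Malignancy, outpatient | No | No |
| Acute kidney injury, outpatient | Yes | No, though laboratory values can reveal it |
| New-onset diabetes, outpatient | In one of several criteria | No, though laboratory values can reveal it |
| Hospitalization | Yes | Yes |

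In the other direction, three list entries match no non-fatal outcome: outpatient cardiac catheterization, outpatient echocardiography or nuclear imaging, and new-onset heart failure. Their only link to 3.E.2 is as background to a cardiovascular death.

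The emergency-visit row is the clearest. The outcome requires under 24 hours and the list requires over 24 hours, so no visit can satisfy both. Such a visit comes within scope only by another entry, for example an infection given parenteral antibiotics.

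Next, the routes outside the list:

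- Visits and calls update medical history and ask about possible outcome events (3.C.2, 3.D.1). These rest on the participant's account.
- Medications since the last visit are listed (3.E.6.b). They can flag an anticoagulant or antibiotic course but do not state a diagnosis.
- Billing searches are run only at selected sites with electronic access (3.E.2.a).
- The national files are named for vital, ESRD and transplant status (3.E.2.a).
- Text-message reports of infection cover cNEPTUNE only, for the first year.
- Source documents may be required (opening of 3.E.2), and records permission is held and renewed annually (3.C.2, 4.J). Neither sits easily with a scope described as limited.

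For size, let p be the share of an outcome managed without a listed event, q the share of that care given outside the center, and r the share of those events recovered by the other routes. The under-documented share is p × q × (1 − r). It is zero if r = 1 and p × q if r = 0. The protocol supplies none of the three values.

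For comparisons, suppose two groups have the same true rate and capture fractions c1 and c2. The observed rate ratio is then c1/c2, which differs from 1 whenever capture differs. The direction depends on which group receives more care outside its center, so it cannot be stated in advance.

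**The case against.** A reader might infer that outpatient events outside the list go uncounted, so that complication rates are biased low by some definite fraction. The protocol does not support that. No section says that an event without a study-acquired record is dropped. 3.E.2.a limits the collection of records, not the counting of events, and a documented diagnosis is not defined as one found in a record obtained under that section. A site could count an outpatient thrombosis from its own chart, from source documents requested under 3.E.2, or from the participant's report. 4.A.2.a expects these diseases to be diagnosed and treated in tertiary nephrology programs, so some related care will be in the site chart. The contact details collected for non-hospitalized events are also what a records request needs.

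A reader might also extend the point to cancer. It is weaker there: malignancy is not defined as documented, and it is not part of the Hypothesis 7 composite. Nor are the cardiac entries necessarily a mistake, since they could help classify a cause of death.

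These objections stand as far as they go. They remove any claim of certain or quantified undercounting. They do not remove the mismatch. If the broader access in 3.E.2 and 4.J governs, then the word limiting the scope in 3.E.2.a is wrong. If 3.E.2.a governs, some outcomes defined as documented have no assured way of being documented when treated elsewhere. Sites are left to choose between the two readings.

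**Conclusion.** The mismatch is established from the text and needs no assumption. Outpatient thromboembolic events, oral-only infections of at least 72 hours, and emergency or observation visits under 24 hours are outcomes outside the record-acquisition list. Three cardiac entries on the list are not non-fatal outcomes. The limit also conflicts with the access allowed in 3.E.2 and 4.J.

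The consequence is conditional. If sites follow 3.E.2.a literally and some of this care is given outside the center, those events are liable to be under-documented, unevenly by site and care setting. The Hypothesis 7 results for thrombosis and infection are then exposed. The size cannot be derived from the protocol, and any percentage would rest on invented inputs. The point concerns secondary outcomes; the primary proteinuria and eGFR outcomes rest mainly on laboratory measurements and do not turn on this list.

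**What to change.** Replace the list in 3.E.2.a with the clinical events of 3.E.2 that need documentation: thromboembolism, infection as defined in item (4), emergency or observation visits under 24 hours, acute kidney injury, malignancy, hospitalization, ESRD and death. Reword the limiting sentence so that it agrees with the source-document provision at the start of 3.E.2 and the authorization in 4.J. Keep the cardiac entries only if they are needed to classify cause of death, and say so. Reporting oral-only infections separately from those with parenteral treatment or admission is optional.

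The cost is a change of wording in the protocol and any matching procedures, plus some additional record requests. The records permission already taken and renewed annually should cover these. Dropping unneeded cardiac requests would offset part of the work.
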